5.0 Study Procedures

The procedures and/or interventions conducted as part of this research are low risk, educational interventions. Elective induction, or induction of labor absent medical indication is an evidence-based aspect of routine pregnancy care that has been endorsed by the OBGYN professional society guidelines as being reasonable to offer since 2018. In clinical practice, the way that this option is offered is currently highly variable and driven by the provider rather than by the patient's preferences and goals. The intervention in this study will be the viewing of standardized information about elective induction of labor prior to making their decision about this option with their provider. Questionnaires will be utilized to understand the impact of the educational intervention on decision quality and the feasibility and acceptability of the intervention.

We will prospectively enroll 60 nulliparous people (approximately 30 at USF and 30 at the Ohio State University) planning vaginal delivery with singleton, vertex pregnancies at 36-38 weeks who do not have a medical indication for IOL to view the DST. During their enrollment face-to-face interview, they will review the DST and complete pre- and post-DST viewing questionnaires. We will conduct telephone interviews a few days later but before 39+0 weeks, and again 2-4 weeks postpartum. During these interviews, we will collect information on the acceptability of the tool and decision quality. We also will include an open-ended question in the postpartum interview to obtain feedback on topics and information the participants wish had been included in the DST.

At the time of enrollment, written informed consent will be obtained by the study research coordinator. The consent form will include information about the purpose of the study, the nature of the subject's participation, the possible risks and discomforts associated with participation, the potential benefits of participation, a statement of the voluntary nature of participation, and a description of the mechanisms used to ensure confidentiality. A study eligibility checklist will be completed prior to any study procedures. Parental consent will be obtained to review the medical records of the infants. Assent is not appropriate given the clinical scenario (review of infant medical records).

- Participation will consist of one face-to-face enrollment interview and two follow-up telephone interviews, along with permission to access the patient's medical chart. Patient-reported data will be collected at 4 time points: at the beginning of the enrollment interview, prior to DST viewing (T1); at the conclusion of that interview, post DST viewing (T2); during a telephone interview at 38-39 weeks gestation, by which time

the decision to undergo or forego elective IOL at 39 weeks will have – or will be close to having been made (T3); and during second telephone interview 2-4 weeks postpartum (T4).

- Participants will initially view the DST on a tablet during the enrollment interview. At the conclusion of the interview, they will be provided with a unique link so that they can revisit the DST content from their personal phone, tablet, or computer if desired.
- During the enrollment interview (T1), we will administer a sociodemographic questionnaire and assess the participant's health literacy level using the Newest Vital Sign (NVS) measure. We also will ask a series of questions related to her inclination to undergo elective IOL at 39 weeks, her attitudes and beliefs about this intervention, her desire for shared decision making in this context, and her feedback regarding the decision tool.
- Attitudes and beliefs (T1, T2, and T3) will be assessed by presenting a series of statements for which participants will be asked to indicate the extent to which they agree or disagree. To measure decisional conflict (T2 and T3), we will use O'Connor's Decisional Conflict Scale, a measure that assesses patients' uncertainty in making a health-related decision, factors that contribute to this uncertainty; and whether they feel their decision making was effective). To measure DST satisfaction (T2, T3, and 2-4 weeks postpartum (T4)), we will use an adapted version of a 3-item intervention-satisfaction scale that we have previously used based on a measure developed by Barry et al. We will use the SDM-9 to measure shared decision making (T3 and T4). During T4, we also will administer the 6-item Birth Satisfaction Scale-Revised Indicator (BSS-RI), which measures stress and emotional response to labor and birth, as well as the Labor Agentry Scale, which measures expectations and experiences of personal control during childbirth and was one of the outcomes measured in the ARRIVE trial. We will include an open-ended question asking what else, if anything, the pregnant person would have wanted to know at the time she made her decision. Outcomes obtained via chart review after delivery will include uptake of elective IOL at 39 weeks, delivery mode undergone (vaginal or cesarean), hospital length of stay (prior to and after delivery), and clinical outcomes (gestational age at delivery, preeclampsia, gestational hypertension, and maternal and neonatal outcomes).
- During the initial face-to-face visit, we will ask participants their preferences for scheduling phone follow up interviews so we can streamline the process as much as possible. Follow up questionnaires can be completed independently via RedCap survey

T1: Prior to DST viewing	T2: Post DST viewing	T3: 38-39 weeks gestation	T4: 2-4 weeks postpartum

 • Sociodemographics, health literacy • IOL inclination • IOL attitudes • Desire for shared decision making • Provider preferences and social norms 	
 • IOL inclination • IOL attitudes • Decisional conflict • DST impact and satisfaction 	
 • IOL inclination • IOL attitudes • Desire for shared decision making • Provider preferences and social norms • Decisional conflict • Shared decision making • DST impact and satisfaction 	
 • Shared decision making • DST impact and satisfaction • Birth Satisfaction Scale • Labor Agentry Scale • Things you wish you had known (open ended)

link; an appointment will be scheduled so that the participants can ask questions if needed. Clinical outcomes will be obtained via chart review after delivery.

- **Subject Costs and Compensation:** The face-to-face interview will take approximately one hour (participants will be remunerated with \$40); telephone interviews will take 15 minutes (\$20 each).

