1.0 Study Summary

Study Title	Should I have an Elective Induction? The SELECTION Study
Study Design	Single arm pilot study of feasibility and acceptability of a decision support tool (DST) for elective induction of labor (IOL).
Primary Objective/Purpose	The goal of the proposed study is to perform a pilot test of a patient-centered DST to help women and providers work together in making informed, shared decisions regarding whether or not to opt for elective IOL at 39 weeks gestation
Secondary Objective(s)/Purposes	This study will provide the information needed to plan a randomized trial of the DST for support of the equitable offer of induction of labor.
Research Intervention(s)	Exposure to the decision support tool
ClinicalTrials.gov NCT #	NCT05838313
Study Population	Nulliparous people with singleton, vertex pregnancies at 36-38 weeks who are planning vaginal delivery and do not have a medical indication for induction of labor
Sample Size	60
Study Duration for individual subjects	Approximately 2 months
Study Specific Abbreviations/ Definitions	DST: decision support tool IOL: induction of labor CD: cesarean delivery

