4.0 Study Intervention

The Elective Induction of labor decision support tool is viewed on a tablet, phone, or computer. It includes information regarding induction of labor, the potential benefits and risks of induction and expectant management, as well as values clarification questions to help people to think through what matters most to people as they consider their decision. In this single arm pilot trial, all participants will view the decision support tool.

The current project is the third part of a three-part study funded by the NIH. The overall goal of the project is to develop a patient-centered decision support tool to help women and providers work together in making informed, shared, values concordant decisions regarding whether or not to opt for elective IOL at 39 weeks gestation.

We have continued to improve upon the process that our group has used to develop other patient-centered prenatal care-related DSTs, which have been tested in NIH-funded, multicenter, randomized clinical trials among English- or Spanish-speaking pregnant women (R01HD078748, R01HD04968). The design process we have used to develop our DSTs follows the standards put forward by the International Patient Decision Aids Standards (IPDAS) Collaboration, using a systematic development process based on the IPDAS quality checklist. We utilize a patient-centered approach, which always begins by examining the needs, desires, and behaviors of the target population. We rely on published, validated literature for the information included in the decision support tools and utilize an iterative process to obtain input from patients and health care providers regarding their views on informational and decision-support needs. Using this patient-centered design approach, our designers work with researchers, providers, and patients to leverage the expertise of all parties in ways that exceed standard expectations for the engagement of these parties in research. This approach allows us to better connect with the people who are the center of our research, and enables quick and effective transformation of data into actionable ideas/tools.

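### The Decisional Conflict Scale is given only after the tool has been viewed, so the pilot cannot describe a before/after change on it or supply pre-tool values for a baseline-adjusted trial; adding it at T1 is an optional, cheap improvement

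*Combined protocol and SAP*

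**What the plan says.** In section 5.0 Study Procedures the text reads "To measure decisional conflict (T2 and T3), we will use" the Decisional Conflict Scale. The table of measures by time point lists decisional conflict under T2 and T3 and not under T1, and the description of the T1 questions does not mention it.

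T1 is the only time point before viewing. T2 comes "at the conclusion of that interview, post DST viewing (T2"). T3 is a telephone interview at 38-39 weeks, by which time the decision will have been made "or will be close to having been made (T3"). Section 4.0 Study Intervention states: "In this single arm pilot trial, all participants will view the decision support tool".

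Other measures are treated differently: "Attitudes and beliefs (T1, T2, and T3) will be assessed", and the table shows inclination toward induction at the same three points.

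The relevant aims are in section 1.0 Study Summary ("This study will provide the information needed to plan a randomized trial of the DST") and section 5.0 Study Procedures ("Questionnaires will be utilized to understand the impact of the educational intervention on decision quality"). The latter section adds: "During these interviews, we will collect information on the acceptability of the tool and decision quality". Section 10.0 Analysis Plan tests no hypothesis. It gives the primary goal as acceptability, feasibility of recruitment and retention, and finalizing measures, and it plans descriptive summaries with confidence intervals and trajectories over time.

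**The concern.** With no control arm, the only contrast a measure can offer is within person. For this scale the first measurement follows the intervention, so its trajectory starts too late to show any movement around viewing. The plan collects pre-tool values for inclination and attitudes and gives no reason for treating this scale differently.

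Three things go unobserved: the change from before to after viewing, the level and spread of decisional conflict before viewing, and the correlation between a pre-tool score and follow-up. The last is the quantity a planner would use to size a trial that adjusts for baseline. None of them can be recovered later for these 60 people.

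**Working it through.** **Schedule.** The text, the table and the description of T1 all agree: T2 and T3 only. Everyone views the tool between T1 and T2. Participants with a pre-tool score: 0 of 60.

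**Plan's own figure.** The sample size of 60 carries no effect size, SD, alpha or power, so there is nothing to reproduce beyond the site split, 30 + 30 = 60.

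**Assumptions, none from the documents.** Correlation rho between pre-tool and follow-up scores of 0.3, 0.5 or 0.7; equal SDs at the two time points; loss of 0 to 20% (60 or 60 × 0.8 = 48 pairs); for the future trial, a 0.3 SD difference, 80% power and two-sided 5%.

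**1. What the plan already gives.** The 95% CI half-width for a mean is t(0.975, n-1)/√n. With n = 60 this is 0.258 SD; with n = 48 it is 0.290 SD. The 95% CI for an SD, with n = 60, runs from √(59/χ²(0.975, 59)) = 0.848 to √(59/χ²(0.025, 59)) = 1.220 times the estimate. The T2-to-T3 change is also estimable.

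**2. What a T1 score would add.** The half-width for a paired change is t(0.975, n-1) × √(2(1 - rho)/n), in SD units:

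| rho | 60 pairs | 48 pairs |
|---|---|---|
| 0.3 | 0.31 | 0.34 |
| 0.5 | 0.26 | 0.29 |
| 0.7 | 0.20 | 0.22 |

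The T1 SD would be known to within the same 0.85 to 1.22 factors with 60 people.

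**3. Consequence for a baseline-adjusted trial.** Unadjusted, n per arm = 2 × (1.960 + 0.842)²/0.3² = 174.4, rounded up to 175. Adjustment multiplies 174.4 by 1 - rho²:

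| rho | 1 - rho² | n per arm |
|---|---|---|
| 0.3 | 0.91 | 159 |
| 0.5 | 0.75 | 131 |
| 0.7 | 0.51 | 89 |

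**4. How well the pilot would pin rho down.** Fisher z 95% CI for an observed rho of 0.5:

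- 60 pairs: 0.282 to 0.669, so 1 - rho² runs from 0.921 to 0.552, or 161 down to 97 per arm.
- 48 pairs: 0.252 to 0.687, so 1 - rho² runs from 0.937 to 0.529, or 164 down to 93 per arm.

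A planner working from the lower confidence limit therefore goes from 175 to 161 or 164, a saving of 14/175 = 8% or 11/175 = 6%.

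**The case against.** The strongest reply is that the schedule looks deliberate and fits a feasibility pilot. The text and table agree, no hypothesis is tested, and the primary goal does not need this score. Inclination and attitudes already give before/after information. No section says that the future trial will use this scale, power on it or adjust for baseline, and a comparison of post-tool scores can be planned from the T2 or T3 SD. All of this stands, and it makes the point an optional improvement.

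Further limits also stand. The pilot's correlation would come only from people who viewed the tool and could differ in a control arm. T1 and T2 fall in one visit of about an hour, so repeating items could affect both the T1-to-T2 change and the T1/T2 correlation. The documents do not show the items, so it cannot be assumed that all of them can be answered before viewing.

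A reader might infer that the schedule contradicts the aim of understanding impact on decision quality. The documents do not support that. They do not define decision quality or equate it with decisional conflict, and they say it is collected during interviews that are most naturally read as the follow-up calls.

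A reader might also infer that the randomized trial cannot be planned, or that the omission costs the gap between 175 and 89 per arm. The first fails because the post-tool SD is available. The second needs rho = 0.7 to be taken as known.

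What survives is narrower: for this one scale, a descriptive change and a rough planning input are lost, and collecting them would need only one more administration at an existing visit.

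**Conclusion.** The concern holds as a limit on what this scale can show. As scheduled, it yields post-tool levels and a T2-to-T3 course, with no before/after change and no pre-tool level, spread or correlation with follow-up. The acceptability and feasibility goal is untouched.

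The planning cost is conditional on a future trial that uses this scale and adjusts for baseline. Under the assumptions above, a realistic gain from knowing rho roughly is 6 to 8% of the sample size for a cautious planner who observed 0.5, and more only if the correlation is high and well supported. A T1 score would still not give a causal effect, because there is no control arm. The reading of the schedule is certain; the size of the planning benefit rests wholly on assumed values.

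**What to change.** Optional, at low cost:

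- **Section 5.0 Study Procedures.** Give the time points for decisional conflict as T1, T2 and T3, and add it to the T1 column of the table. First check that the items can be answered before viewing. If some cannot, use the items common to T1 and T2 for the paired comparison.
- **Section 10.0 Analysis Plan.** Add text such as: *For decisional conflict we will report the T1 mean and SD; the paired T1-to-T2 and T1-to-T3 changes with 95% CIs and the number of pairs; and the T1/T3 correlation with its 95% CI as the main planning value. These results are descriptive and do not estimate a causal effect. The T1-to-T2 change and any T1/T2 correlation may reflect same-visit carry-over. The T1-to-T3 change also spans the period in which the decision is made. The correlation comes only from people who viewed the tool and may differ in a control arm.*
- **If T1 is not added.** State in section 10.0 that decisional conflict will be reported only as a post-viewing level and its T2-to-T3 course, not as a change caused by or following the tool.

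Cost: added time in the one-hour enrollment visit (the scale's length is not given), possible carry-over, edits to the text and table, and an IRB modification. No extra participants or visits are needed. The fallback costs one sentence.

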6.0 Risks and Protections against Risks

Risks or discomforts for the pregnant people are limited to those that might be incurred as a result of discussing sensitive or potentially troubling information as well as potential risks to confidentiality.

Some of the questions addressed by the proposed study are of a sensitive nature and require the subject to consider outcomes that they may find distressing (e.g., pregnancy complications). It is possible that these topics may induce anxiety among respondents. While this has not been a problem in our prior studies of potentially anxiety-provoking decision tools (including tools used by pregnant women that discuss the possibility that their fetus may be affected by a serious disorder or that they will experience a pregnancy loss and be unable to give birth in the future) it is important that we carefully consider how we will minimize the likelihood of this problem and how we will assist our participants if their participation does result in some anxiety.

First, all participants will be informed, prior to participation, that they are free to terminate their participation at any time or to decline to answer any questions or participate in any part of the study. During the consent process, we will ensure that the participant understands this principle and they feel free to exercise their option at any time. Participants will have access to their obstetric providers to discuss their concerns as well as to the clinician investigators at each site.

Additionally, participants will be informed that if they develop any feelings of anxiety at any time during their participation, they should contact the study team (they will be provided with an access number). These participants will be contacted within 24 hours by one of the study clinician-investigators. All of these clinicians have extensive clinical experience and are highly skilled in dealing with patients who develop anxiety during their medical care. They are available at any time via their hospital on call system. The responding physician will contact the participant and discuss their clinical situation. If necessary, the physician will meet with the participant in person at their clinical office or the office of the participant's primary obstetric provider (wherever the participant feels most comfortable).

If a participant's symptoms require more intensive intervention, this will be arranged by the clinician-investigator to ensure that the participant will receive all necessary care to address whatever symptoms might occur. The physician-investigator who becomes involved with any participant over any anxiety symptoms will continue to monitor the patient (either by phone or in person) until all symptoms have abated.

Each contact will be reported and tracked as an adverse outcome.

In sum, we have an extensive support infrastructure for the management of mental health issues that arise in the course of study participation. As noted, we have conducted similar studies in the past and have not had problems with anxiety, but we are fully prepared to deal with this possibility at any time should it occur.

Undue influence will be minimized by emphasizing the voluntary nature of the study in all recruitment materials and personal communications. Participants also have the alternative not to participate in the study. Non-participation will not affect clinical care. Participants will be consistently reminded that responses to any queries deemed sensitive or uncomfortable (e.g. country of origin/ immigration status, income, previous history of abortion) should be considered optional, and they may decline to answer any question(s) and can refuse to continue the study at any point. Participants also will be reassured that neither their opportunities for continued health care nor their relationships with health care providers will be jeopardized by study participation.

7.0 Data Management and Confidentiality

We will take extensive precautions to maintain participant confidentiality throughout the study. First, lists of individuals who will be participating will be kept in a locked drawer and in password protected computer files in the office of the study coordinator at each site. Used consent forms will also be locked in a filing cabinet in the office of the study coordinator. Confidentiality of all study-related records will be maintained in accordance with State and Federal laws.

Three databases will be maintained for the study: 1 and 2) Site specific “participant tracking” databases will contain all identifying information that will permit locating participants for their interviews, ensuring that interviews are completed on time, and performing chart reviews. It will include demographic information for all patients who do not meet the eligibility criteria or who decline participation, along with their reasons for refusal (to permit comparisons between those who do and do not enter the study). 2) A single “study data” database will contain all project-related data used for the analyses. Participants will be identified only by a code number in the study database.

Obstetric clinic schedules will be reviewed to screen for eligibility, so that only subjects meeting eligibility criteria will be approached. We will keep the minimum information necessary (Name, MR#, appointment date and time) in the recruitment database so that we know who has an appointment and can make sure recruitment materials are available when they are in clinic. People who decline will be marked as declining so that they are not approached again. Records reviewed will only be from people who are actively receiving prenatal care and scheduled for appointments within the 4 weeks prior to the timeline for the study. Only study staff will have access to the RedCap database. Because we can only identify eligible patients based on medical record review, it is not practical to obtain consent prior to the approach. Identifiers will be removed within 6 months and only information needed to inform the CONSORT diagram will be maintained.

Only the PI and a limited number of study personnel will have access to identified information which will be encrypted and stored on a secure server. As in our previous studies, only code numbers will be used and no individual identities will be retained in the analysis or publications. Data confidentiality will be ensured by using only a coded participant acronym and code number to identify respondents on the data-collection forms. All data will be entered into RedCap database that will have logic, range, and error checking, and will be kept on an encrypted, security enabled network. Only researchers involved with the study will have full access to subject identities. Datasets used for analysis will be de-identified. As per the USF

guidelines, records will be maintained for 5 years after the study is complete and at that time we will destroy records linking participants' names to study ID numbers. Participant identities will not be revealed in any publication that may result from the proposed study.

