5.0 Recruitment

Each site will utilize the same recruitment methods that we have used successfully in prior studies of pregnant people. We will ensure that all necessary human subjects' reviews and approvals are obtained prior to implementation at any recruitment site.

Potentially eligible participants will be identified by reviewing outpatient charts to identify pregnant people who meet the eligibility criteria. At all sites, both academic and "private" practices are associated with an academic health system, and as such, with IRB approval, study staff is able to remain HIPAA-compliant when they pre-screen patients.

At USF, eligible people will receive a letter describing the study, signed by a leadership representative of their OB practice (as many patients do not have a single provider they see for prenatal care, but rather see a team of providers). A stamped return "opt in/out" card will be included, which the recipients can return to indicate that they are either interested or not interested in hearing from the study staff. The site-specific interviewer's telephone number also will be included for each recipient's use if they prefer to use this method of communication. Respondents who check "opt in" will be called/contacted by the method they state they prefer. Those who opt out will not be contacted. A study staff member will come to a subsequent visit at which time the clinical staff will ask the participant if they would be willing to discuss the study and assess their eligibility and interest in participating. The "opt out" mechanism has been shown to yield a more diverse group of participants than the "opt in" approach, and, in our many studies of diverse populations, has been highly effective in recruiting participants for

studies that require conducting face-to-face interviews with pregnant people at specific gestational ages.

At OSU, eligible people will receive a brochure detailing the study. Those who are eligible and interested will be contacted to set up an enrollment interview.

Participants will be identified starting at 32-34 weeks with the goal of scheduling the initial study visit between 36+0 and 38+0 weeks gestation to allow time to view and consider the information in the decision tool prior to making a decision regarding whether to proceed with an elective induction at 39+0 to 39+6 weeks gestation.

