10.0 Analysis Plan

Statistical Design and Power

As a pilot study, there are no hypotheses to be tested; therefore formal sample size calculations are not appropriate.

This is a single arm prospective clinical trial to collect pilot data for planning a future study of the impact of the Elective IOL DST, the intervention of interest, on induction rates, cesarean delivery rates, decision quality and resource use. The primary goal of this pilot is to determine the acceptability of the Elective IOL DST, to assess the feasibility of recruiting and retaining study participants in anticipation of future effectiveness and implementation studies, and to finalize outcome and other measures. The descriptive analyses planned include cross-sectional analyses, which will consist of profiles of the sample, including examination of means and proportions, measures of variability, and confidence intervals around these statistics. We also will investigate relationships within and between measurement domains (e.g. demographics, outcomes), although these will only be exploratory in nature. In addition, we will describe the trajectories of participant responses across time.

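### Does Section 7.0 discard the data it promises for comparing people who enroll with those who do not?

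*Combined protocol and SAP*

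**What the plan says.** Section 7.0 declares three databases: one participant tracking database for each of the two sites, and one coded study-data database. Of the tracking databases it says: "It will include demographic information for all patients who do not meet the eligibility criteria or who decline participation". Reasons for refusal are recorded as well, and the purpose is given as "to permit comparisons between those who do and do not enter the study".

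The following paragraph deals with screening of clinic schedules. It says "We will keep the minimum information necessary (Name, MR#, appointment date and time) in the recruitment database", so that staff know who is due in clinic and can have recruitment materials ready. Decliners are flagged so that they are not approached again. The paragraph closes by saying that identifiers are removed within six months and that "only information needed to inform the CONSORT diagram will be maintained". Later in the same section, "records will be maintained for 5 years after the study is complete", after which the link between names and study numbers is destroyed.

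Section 10.0 plans descriptive profiles of the sample with confidence intervals. It does not mention a comparison of enrolled and non-enrolled people.

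**The concern.** The recruitment database is not one of the three declared databases, and its relation to the tracking databases is not stated. The six-month rule names neither a database nor a starting point. Because study records are kept for five years, the shorter rule seems aimed at people who were screened but not enrolled, and these are the people whose demographics were promised. If staff applied the short field list and the CONSORT-only rule to all of them, the comparison would have no source data.

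That would bear on a stated goal. Section 10.0 includes in the primary goal "to assess the feasibility of recruiting and retaining study participants in anticipation of future effectiveness and implementation studies", and the Study Summary says the pilot will inform a randomized trial concerned with equitable offer of induction. Section 5.0 (Recruitment) says that the opt-out "mechanism has been shown to yield a more diverse group of participants than the" opt-in approach, so the protocol itself holds that the recruitment route affects who enrolls. The sites use different routes. USF sends a letter with a reply card and follows up at a clinic visit. OSU sends a brochure, after which "Those who are eligible and interested will be contacted to set up an enrollment interview". Without demographics on people who did not enroll, the pilot could not describe whom either route missed.

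**Working it through.** The main question is one of reading, so the two paragraphs of Section 7.0 are set side by side.

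| Point | Tracking-database paragraph | Clinic-schedule paragraph |
|---|---|---|
| Purpose | Locating participants, timing interviews, chart review, comparing enrolled with non-enrolled | Knowing who has an appointment and having materials ready |
| Content for people not enrolled | Demographics and refusal reasons | Name, record number, appointment date and time, decline flag |
| Retention | No separate limit stated | Identifiers removed within six months; CONSORT information kept |

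1. **Capture.** None of the four listed items is demographic. The list is given as the content of the recruitment database, however, and the text does not say that this database replaces the tracking databases. Read as an appointment list, it leaves the demographic promise intact.
2. **Retention.** The six-month sentence ends the clinic-schedule paragraph and may cover that list alone. If it reaches further, it still sets a deadline for removing identifiers and does not forbid a table made before the deadline. Refusal reasons could also survive as CONSORT information.
3. **Analysis.** Section 10.0 is generic and lists no specific contrast or variable. Its silence does not cancel a purpose stated in Section 7.0.

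The plan gives no figure on this point to reproduce. To see how much the comparison could show with complete data, take the most favorable case, in which the number of non-participants is so large that it adds no sampling error. The 95% half-width for the difference in a proportion then cannot fall below 1.96 × √(p(1 − p)/n). The inputs are n = 60 overall and about 30 per site (Section 5.0, Study Procedures), and p from 0.3 to 0.5, which is an assumption.

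- n = 60, p = 0.3: 1.96 × √(0.21/60) = 0.116
- n = 60, p = 0.5: 1.96 × √(0.25/60) = 0.127
- n = 30, p = 0.3: 1.96 × √(0.21/30) = 0.164
- n = 30, p = 0.5: 1.96 × √(0.25/30) = 0.179

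So the comparison can reveal only large imbalances, about 12 to 13 points overall and 16 to 18 points within a site at best. These figures describe the precision of the comparison if the data exist. They do not measure the harm done by the wording.

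**The case for a change.** The strongest case for a change is that the favorable reading is plausible but not confirmed. Two coordinators could follow the same text in good faith and keep different data, and anything purged before it is tabulated may be lost. Non-response may be a main route to non-enrollment at OSU, and the promise covers only ineligible people and decliners. One rule, de-identified rows for everyone not enrolled, and a comparison by site would close the gap at little cost.

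The first part stands: the text does not say which database the six-month rule covers or when the period starts. The rest goes further than the protocol's own commitment. Keeping individual rows on non-responders means holding data on people who have not consented, against the protocol's undertaking to hold only what is necessary. The return would be a comparison with the precision shown above. The pilot would also not be left without information on recruitment. Sociodemographics and health literacy are collected from every participant at T1, so the enrolled group can be described by site, and counts and refusal reasons can be reported for the feasibility goal.

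**Conclusion.** The ambiguity is real but minor, and no change to the plan is needed. On a natural reading, the short field list and the six-month rule govern the appointment list, and the promised comparison keeps its data. On the stricter reading, it survives if the table is made before identifiers are removed, which study staff can arrange without altering the design.

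This rests on two assumptions: that the tracking databases are filled as Section 7.0 describes, and that staff do not purge before tabulating. If both failed, the loss would be one descriptive table on representativeness. The sample size of 60, the acceptability and retention results, the patient-reported measures and the chart outcomes would be untouched. Broader collection on people who did not enroll is a matter of preference, with a privacy cost, and its absence is not a defect in the plan.
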